12 ADVERSE EVENT REPORTING

12.1 Definitions

12.1.1 Adverse Event

For the purposes of this trial an AE is defined as:

Any new unfavorable/unintended signs/symptoms (including abnormal laboratory findings when relevant), or diagnosis or worsening of a pre-existing condition, which occurs following screening (Visit 1) and at any point up to the post-treatment, final safety follow-up visit (Visit 11), which may or may not be considered to be related to the IMP. Any event that is the result of a trial procedure must be recorded as an AE.

Surgical/Investigational procedures are not AEs. The medical reason for the procedure is the AE. Elective hospitalizations for pre-trial existing conditions or elective procedures are not AEs. The exception may be if the patient has an AE during hospitalization which prolongs their scheduled hospital stay in which case it would be considered a SAE (refer to [Section 12.2](#)).

If reporting a fatal event, the SAE term should be the underlying cause of the death (e.g., disease or medical condition leading to death).

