12.5 Causality Assessment

Causality assessment is required for all AEs and SAEs. Causality assessment must only be assigned by the investigator. All cases judged as having a reasonable suspected causal relationship to the IMP must be reported as such. The expression "*reasonable causal relationship*" is meant to convey in general that there are facts (evidence) or arguments to suggest a causal relationship.

The following question which must be answered by the investigator for all AEs is used to capture the reasonable causal relationship of an event to the IMP:

"In your opinion is there a plausible relationship to the IMP?" The answer is either "yes" or "no".

Events that start before the first dose of IMP (pre-treatment) should be considered as not causally related. Where a pre-treatment event worsens in severity following the first dose of IMP, a new event record should be entered into the eCRF.

Study Code: GWND18064

EudraCT Number: 2018-003370-27

Clinical Protocol 4.1, 07Jul2020 (duplicate synopsis removed)

Considering the explanation given above, investigators are strongly encouraged to express their opinion on what the cause of an AE might be. For individual patients, the investigator is usually in the best position to assess the underlying suspected cause of an AE. For all AEs and especially SAEs, it is important that the investigator assess not only the possible role of the IMP but also other potential contributing factors. Factors for consideration of the underlying cause may include:

- Medical and disease history.
- Lack of efficacy/worsening of treated condition.
- Concomitant or previous treatment.
- IMP discontinuation.
- Protocol-related procedure.

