- Continuing.
- Patient died.

D) Severity

When describing the severity of an AE the terms mild, moderate, or severe should be used. Clinical judgment should be used when determining which severity applies to any AE.

If the severity of an AE fluctuates day-to-day, e.g., a headache or constipation, the change in severity should not be recorded each time; instead, only the worst observed severity should be recorded with AE start and stop dates relating to the overall event duration, regardless of severity.

A severe AE is not the same as a SAE. For example, a patient may have severe vomiting, but the event does not result in any of the SAE criteria above. Therefore, it should not be classed as serious.

E) Causality

See [Section 12.5](#) above.

Study Code: GWND18064

EudraCT Number: 2018-003370-27

Clinical Protocol 4.1, 07Jul2020 (duplicate synopsis removed)

F) Action Taken with Trial Medication

This question refers to the action taken with the IMP due to an AE. The action with the IMP must be classed as:

- Not applicable, patient is not taking IMP.
- Dose not changed.
- Dose reduced.
- Trial medication interrupted.
- Trial medication stopped.

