13.6.3.2 Adverse Events

Adverse events will be coded according to the Medical Dictionary for Regulatory Activities dictionary.

A treatment-emergent adverse event (TEAE) is one that started, or worsened in severity or seriousness, following the first dose of IMP.

Descriptive presentations of TEAEs will be given by preferred term and SOC for the safety analysis set. The number of patients reporting at least 1 TEAE will be provided.

The following summaries will be produced as a minimum:

- All-causality TEAEs.

Study Code: GWND18064

EudraCT Number: 2018-003370-27

Clinical Protocol 4.1, 07Jul2020 (duplicate synopsis removed)

- Treatment-related AEs.
- All-causality TEAEs by maximal severity.
- All-causality serious TEAEs.
- Treatment-related serious TEAEs.
- TEAEs reported as leading to permanent cessation of IMP.
- Fatal TEAEs.

In the presentation of safety data, data from the GWP42003-P dose groups will be presented separately and compared with placebo. This will allow the possibility to explore any effects of the dose of IMP on safety endpoints.

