##### 6.1.7.1.3 Adverse Events

Missing and/or incomplete dates for AEs will be imputed in a manner resulting in the earliest onset or the longest duration during the treatment period, while ensuring that the start date is not after the stop date, i.e. missing start dates will be imputed as the first day of the month/first month of

the year and missing stop dates will be imputed as the last day of the month/last day of the year, while ensuring that the start date is not after the stop date. Upper and lower limits of imputation will be date of Visit 2 and date of Visit 9, and events occurring on date of Visit 2 will be assumed post-IMP as per [Section 6.1.9.1](#) Stop dates will not be imputed if the AE is ongoing.

The imputation method will be used to determine treatment emergence and time to onset/resolution of an AE, and imputed dates/times will not be presented in AE outputs.

A worst-case approach will be followed in the event of missing severity or causality data. If the severity is missing, ‘Severe’ will be imputed. If causality data is missing for a treatment emergent AE (TEAE), ‘Yes’ will be imputed for the question ‘Plausible relationship to study medication’.

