#### **6.1.9.1 Adverse events**

A TEAE is defined as an AE with a start date on or after the first dose of IMP. If an AE has a partial start date and it is unclear from the partial date (or the stop date) whether the AE started prior to or post first dose of IMP then the AE will be considered treatment emergent. If the start date of the AE is the same as the date of first dose of IMP then the AE will be considered treatment emergent.

A TEAE will be considered treatment-related if the plausibility relationship to IMP is recorded on the eCRF as ‘yes’. If the data on plausibility relationship to IMP is missing then the TEAE will be considered treatment-related.

A TEAE will be considered leading to permanent discontinuation of IMP (leading to withdrawal) if the action taken with IMP is recorded on the eCRF as ‘trial medication stopped’ or the outcome is recorded on the eCRF as ‘patient died’.

A treatment-related TEAEs leading to withdrawal is a TEAE leading to permanent IMP

discontinuation and considered treatment-related as per above definition.

A TEAE will be considered leading to IMP temporary discontinuation if the action taken with IMP is recorded on the eCRF as 'trial medication interrupted'.

A TEAE will be considered leading to permanent IMP dose reduction excluding permanent discontinuation if the action taken with IMP is recorded on the eCRF as 'dose reduced'.

An AE will be considered fatal if the outcome is recorded on the eCRF as 'patient died'.

The time to first onset of AE will be calculated for TEAEs as:

Start date of AE – Date of first dose of IMP + 1

The time to AE resolution will be calculated for TEAEs as:

Stop date of AE – Start date of AE + 1

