All AEs will be listed. Listings will include the start and stop day of the AE, a flag for treatment emergence, and limited demographic information about the patient (age, sex, race and weight at screening). A separate listing will be provided for pre-treatment AEs, serious AEs and events of special interest (see [APPENDIX Appendix 2](#)).

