#### **9.5 Changes in the Conduct of the Trial or Planned Analysis**

After carefully evaluating the study performance and the potential impact of the COVID-19 pandemic to patients and site personnel the Sponsor made the decision to discontinue the trial. The significant challenges to conducting studies in this vulnerable group of patients were magnified by the COVID-19 pandemic leading to the conclusion that it was no longer feasible to conduct this study. As a result the analyses described in this SAP differ from those that were initially intended and presented in the protocol.

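### The SAP defines treatment-emergent AEs by start date alone, so a pre-dose AE that becomes serious on treatment with no change in severity is missing from the TEAE summaries

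*SAP*

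**What the plan says.** Protocol 13.6.3.2 gives three routes to treatment emergence, namely onset, worse severity or worse seriousness after dosing: "A treatment-emergent adverse event (TEAE) is one that started, or worsened in severity or seriousness, following the first dose of IMP".

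SAP 6.1.9.1 keeps only the first: "A TEAE is defined as an AE with a start date on or after the first dose of IMP". The rest of that paragraph deals with partial dates and with events that start on the day of first dose. SAP 6.1.7.1.3 likewise works from dates: "The imputation method will be used to determine treatment emergence and time to onset/resolution of an AE". Nothing else in the SAP brings back a worsening criterion for AEs.

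Two recording rules in the protocol decide which start date an event carries. Section 12.5 says: "Where a pre-treatment event worsens in severity following the first dose of IMP, a new event record should be entered into the eCRF". Section 12.6 D, on severity that varies from day to day, says that "only the worst observed severity should be recorded with AE start and stop dates relating to the overall event duration".

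SAP 9.5 gives a general reason for departing from the protocol, the discontinuation of the trial: "As a result the analyses described in this SAP differ from those that were initially intended and presented in the protocol". It does not mention the TEAE definition.

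**The concern.** The SAP tests no hypotheses, so its descriptive safety tables are a main product of the trial, and nearly all the AE tables in SAP 9.1 are built on the TEAE flag. If the flag ignores worsening, an event that began during baseline and became serious on treatment is classed as pre-treatment. It then drops out of the TEAE and serious TEAE summaries.

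The SAP's own liver enzyme rule in 9.2.1 is built differently. There, a criterion that was unmet at baseline and met at any later time counts as treatment-emergent, so worsening is captured. Discontinuing the trial explains why inferential analysis was dropped. It does not explain a narrower safety definition.

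**Working it through.** There is no figure to reproduce. The check follows each kind of event through the recording rules and then applies the two definitions.

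**Events exposed.** AEs are collected from after Visit 1 (Protocol 12.1.1). Visit 2, where the first dose is given, falls 14 to 28 days after Visit 1 with a window of up to 6 further days (Protocol 9.1.1.2). The exposed onset period is therefore 14 to 28 + 6 = 34 days per patient. A condition already present at screening is not exposed. Its later worsening is itself an AE under Protocol 12.1.1, with onset at the worsening.

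**Classification by case.**

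| Case | How it is recorded | Protocol 13.6.3.2 | SAP 6.1.9.1 |
|---|---|---|---|
| (a) AE starts after first dose | Post-dose start date | TEAE | TEAE |
| (b) Pre-dose AE worsens in severity after dosing, new record made as 12.5 asks | New record, taken to start at the worsening | TEAE | TEAE |
| (c) Pre-dose AE becomes serious after dosing, same severity grade | No new record required; pre-dose start date stays | TEAE | Not a TEAE |
| (d) Pre-dose AE with day-to-day fluctuation that worsens after dosing | 12.5 points to a new record, 12.6 D to a single record | TEAE | Depends on which rule the site follows |
| (e) Pre-dose AE worsens in severity, site omits the new record | Pre-dose start date stays | TEAE | Not a TEAE |

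**Reading the table.** Case (c) is the firm gap. It follows from the written rules even when every site complies. Protocol 12.6 D itself separates severity from seriousness, so a grade can stay the same while an event meets a seriousness criterion, for example through hospital admission. Case (d) is an unresolved conflict between two protocol sections. Case (e) is a compliance failure that the SAP has no check to find.

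**Where case (c) still appears.** SAP 9.1 plans a summary of pre-treatment AEs and a listing of all AEs, and adds: "A separate listing will be provided for pre-treatment AEs, serious AEs and events of special interest". The event can therefore be found, but it is not counted in the TEAE or serious TEAE summaries.

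**What the data can show.** The AE items in Protocol 12.6 A to F are term, start and stop dates, outcome, severity, causality and action taken. No date of worsening, or of becoming serious, is described. Classification of case (c) therefore needs someone to read the record and cannot rest on a date comparison alone. Protocol 12.3 requires SAEs to be entered within 24 hours of discovery or notification, which should help to place the change in time.

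**The case against.** The strongest reply is that data capture already does most of the work. Under Protocol 12.5, a pre-treatment event that worsens in severity becomes a new post-dose record, which the SAP counts. This stands. A reader might infer from the two definitions that on-treatment worsening in general is lost, and the documents do not support that.

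Three further replies also stand, and each limits what can be claimed.

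- **Fluctuating events.** Section 12.6 D concerns day-to-day variation and is meant to stop sites logging every change. It does not say that worsening across the first dose stays in the old record, and 12.5 addresses that situation directly. It would be too strong to say that fluctuating events are definitely missed. The two sections need reconciling.
- **Relatedness tables.** One might expect the missed events to be lost from the treatment-related tables too. Protocol 12.5 says that events starting before the first dose should be treated as not causally related. A single record with a pre-dose start would stay out of those tables under either definition.
- **Direction.** One might infer that the SAP's AE handling leans towards under-counting. Elsewhere it leans the other way. Unclear partial dates and same-day onsets count as treatment-emergent, missing severity becomes severe, and missing causality becomes related. Only the missing worsening criterion works towards under-counting.

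It can also be said that the trial was stopped and its analysis is descriptive. That lowers the stakes, but it does not justify an undeclared change of definition.

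**Conclusion.** The point holds in a limited form. The SAP's TEAE definition is narrower than the protocol's, and the difference is not explained. The certain consequence is that an AE starting between Visit 1 and first dose, and becoming serious on treatment at the same grade, is missing from the TEAE and serious TEAE summaries. A second consequence, for fluctuating events, depends on how 12.5 and 12.6 D are read together.

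The documents give no counts, so the size cannot be calculated. It is probably small, because the onset period is at most 34 days and an event that becomes serious will often rise in severity as well, which triggers the 12.5 record. The events remain in the listings, so the fault lies in the summaries. It should not be read as safety data going unreported.

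This rests on two assumptions: that a new record made under 12.5 carries a start date at the worsening, and that no eCRF instruction outside these documents asks for a new record when only seriousness changes.

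**What to change.** 1. In SAP 6.1.9.1, restore the definition in Protocol 13.6.3.2, so that onset, worse severity or worse seriousness after first dose each make an event treatment-emergent. Refer to the new-record rule in Protocol 12.5.
2. Add a data check that flags AEs with a pre-dose start that were ongoing at first dose and are recorded as serious. Send these to blinded medical review before unblinding, and count as TEAEs those that became serious or worsened after first dose. An event that was already serious before dosing and did not worsen stays pre-treatment.
3. Do not count an event as a TEAE only because an action was taken with IMP. Such an action does not show worsening, and counting on that ground would depart from the protocol definition.
4. Reconcile Protocol 12.5 with 12.6 D for a fluctuating event that began before dosing and worsened after it. The new SAP wording alone cannot recover such an event if it sits in one record, because no date of worsening is described.

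If the narrower definition is intended, SAP 9.5 should declare it and give a reason.

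The cost is one sentence, one data check and slightly higher TEAE counts. SAP 4.2.2 plans no blinded data review meeting, so the medical review of flagged records has to be added as a short step before unblinding.

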9.1.2 Telephone Visits (Safety Follow-Ups)

9.1.2.1 Visits 3 (Day 8), 4 (Day 15), 11 (Day 207)

Visits 3 and 4 will occur 7 and 14 days after randomization (Visit 2), respectively.

Visit 11 will occur 28 days after Visit 10 (or Visit 9 if the patient did not taper) for patients who do not enter the OLE trial (under a separate protocol) or who withdraw from the trial early.

A visit window of \pm 3 days from the scheduled visit date is permitted, except for Visit 11, where a window of + 3 days is permitted, but it is preferred that the visit is performed on the scheduled visit day where possible.

Telephone visits will be conducted and information regarding adherence to the dosing regimen (except for Visit 11), AEs, and changes to concomitant medications will be reviewed by a delegated personnel (the site investigator need only be involved if necessary, e.g., if any concerns are raised during the call). The weekly symptom diary will be reviewed (except for Visit 11).

Visit 11 constitutes the last scheduled safety follow-up. The purpose of the visit is to ascertain the status of AEs continuing after cessation of IMP or any new AEs commencing after discontinuation. All causally-related AEs that result in a patient's premature termination from the trial or are present at the end of the trial should be followed up until a satisfactory resolution occurs; that is, until the AE resolves or is considered clinically insignificant, or until an investigator is satisfied that the AE is not related to IMP and needs no further investigation.

Study Code: GWND18064

EudraCT Number: 2018-003370-27

Clinical Protocol 4.1, 07Jul2020 (duplicate synopsis removed)

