12.3 Reporting Procedures for Serious Adverse Events

All SAEs occurring during the trial must be reported to GW with any other supporting information and recorded in the AE section of the eCRF. Any ongoing SAEs should be followed up until resolution wherever possible. For all deaths, the working diagnosis or cause of death as stated on a death certificate, available autopsy reports and relevant medical reports should be sent to GW promptly.

All SAEs must be recorded in the eCRF within 24 hours of discovery or notification of the event. GW PVD will be automatically notified that an SAE has been recorded. Any additional information required for a case (follow-up or corrections to the original case) will be requested by GW PVD through eCRF queries.

The investigator should continue to document all AEs which occur up to the last formal follow-up observational period (Visit 11). If the investigator subsequently becomes aware of any deaths or a new IMP-related SAE after the last formal follow-up period of the trial, these should still be reported to the GW PVD.

Any other problem discovered after Visit 11 which is deemed to be an unexpected safety issue and is likely to have an impact on patients who have taken part in the trial must be

Study Code: GWND18064

EudraCT Number: 2018-003370-27

Clinical Protocol 4.1, 07Jul2020 (duplicate synopsis removed)

treated as an SAE and reported to the GW PVD. Such post-trial SAEs do not need to be recorded on the patient's eCRF if editing rights to the eCRF have been removed due to final trial data lock. GW PVD may request safety follow-up information after the final trial visit in order to investigate a potential safety issue.

Contact details for the GW PVD are provided at the front of the site files for all trial sites.

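### SAP 6.1.9.1 counts a fatal TEAE that starts after the last dose as leading to permanent discontinuation of IMP, because its death criterion has no dosing condition

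*SAP*

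**What the plan says.** SAP 6.1.9.1 gives two alternative criteria for a TEAE leading to permanent discontinuation, which it also labels leading to withdrawal. Either the action taken with IMP is *trial medication stopped*, "or the outcome is recorded on the eCRF as" *patient died*. The treatment-related version adds only the relatedness condition. The same section sets the two neighbouring definitions:

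- "A TEAE is defined as an AE with a start date on or after the first dose of IMP", with no upper limit tied to the last dose.
- "An AE will be considered fatal if the outcome is recorded on the eCRF as" *patient died*, which is the same field and value as the second discontinuation criterion.

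The protocol fixes how long events are collected and how the action is recorded:

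- Protocol 12.1.1 collects AEs "at any point up to the post-treatment, final safety follow-up visit (Visit 11").
- Protocol 9.1.2.1 places that contact after dosing has ended: "Visit 11 will occur 28 days after Visit 10 (or Visit 9 if the patient did not taper"). It applies to patients who do not enter the open-label extension or who withdraw early.
- Protocol 10 asks patients who stop IMP to stay in the trial and keep attending visits.
- Protocol 12.6 (F) lists five values for the action taken, the first being "Not applicable, patient is not taking IMP".

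Protocol 13.6.3.2 plans a summary of TEAEs reported as the cause of permanent cessation of IMP, and lists fatal TEAEs as a separate summary. SAP 9.1 keeps both tables and adds the treatment-related discontinuation table and the withdrawal rows of the overall AE summary.

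**The concern.** An event that begins after the last dose cannot be the reason the patient stopped. The SAP nevertheless counts it as such if it is fatal, and overrides the eCRF value designed to identify it. The count would reach the discontinuation table, the withdrawal row of the overall summary and, if the event is judged related, the treatment-related versions of both. SAP 6.1.7.1.3 and 6.1.9.1 treat missing causality as related, so an off-drug death with no causality entry would appear as a treatment-related withdrawal.

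These are main tolerability outputs by dose. They could also disagree with disposition: a patient who finished the treatment period and died in follow-up would be a completer under SAP 7.1 and a discontinuation in the AE tables.

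**Working it through.** There is no planned figure to reproduce; this is a check of logic followed by a simple size calculation.

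**1. Apply the rule to every recorded combination.** Protocol 12.6 gives 5 action values and 4 outcomes (recovered, recovered with sequelae, continuing, patient died), so 5 × 4 = 20 combinations.

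| Recorded action | Three non-fatal outcomes | Patient died |
|---|---|---|
| Not applicable (not taking IMP) | not counted | counted |
| Dose not changed | not counted | counted |
| Dose reduced | not counted | counted |
| Trial medication interrupted | not counted | counted |
| Trial medication stopped | counted | counted |

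The rule counts 4 (stopped, any outcome) + 4 (died, any other action) = 8 of 20. Four of the 8 are counted only because the patient died, and one of those four is the not-applicable action.

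**2. Can that combination occur?** Yes, by design. With a taper, Visit 10 is Day 179 and Visit 11 is Day 207, so 207 − 179 = 28 days of AE collection follow the end of taper. Without a taper, Visit 11 is 28 days after Visit 9. Early stoppers who remain have longer. As an illustration, stopping at Visit 5 (Day 29) with a 10-day taper leaves 169 − (29 + 10) = 130 days off drug before Visit 9. Patients who move straight into the extension have no Visit 11.

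**3. Does another passage close the gap?** SAP 6.1.7.1.3 names Visit 9 as an upper limit, but only for imputing missing or partial AE dates. It does not end the TEAE window. No passage limits the death criterion to patients on IMP.

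**4. Size.** SAP 9.1 counts patients, so one additional patient moves a percentage by 100/n points.

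- Planned active arm or pooled placebo, n = 84: 100/84 = 1.2 points.
- Either placebo dose column, which SAP 3.2 also presents for safety, planned n = 42: 100/42 = 2.4 points.
- Curtailed trial: n is not given. If an active arm reached half or a quarter of plan (assumptions; n = 42 or 21), the step would be 2.4 or 100/21 = 4.8 points.

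The step applies to the overall row only if the patient is not already there. Someone who stopped IMP for an earlier AE and later died of a new off-drug event is already counted overall; only a system organ class or preferred term row can change.

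**5. After a change.** Excluding the not-applicable action from the death criterion leaves 8 − 1 = 7 combinations. Using the action field alone leaves 4. Every fatal TEAE remains in the fatal summary either way.

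**The case against.** The best defence is that the death criterion is a reasonable convention. Death on drug does end dosing, and an investigator may leave the action as *dose not changed*; the second criterion catches that case. It resembles the SAP's cautious handling elsewhere, and it can only overcount discontinuations, never hide one. The analysis is descriptive, fatal TEAEs have their own table, serious AEs are listed separately and all collected data are listed, so a careful reader could spot an affected patient.

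The argument for on-drug deaths stands. The rest does not remove the point. The worst-case rule in SAP 6.1.7.1.3 covers missing severity and causality, whereas here a recorded value is overridden. A separate fatal table and listings show the death but do not correct the discontinuation counts.

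A reader might also infer that every death after the last dose is wrongly reported as a withdrawal, or that each one raises the overall rate by 1.2 points. The documents support neither. If IMP was stopped for the event that later proved fatal, the action is *trial medication stopped* and the count is right, however long after the last dose the patient died. The increment also disappears from the overall row for a patient already counted as an AE discontinuation.

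**Conclusion.** The point holds in a narrow form. A fatal TEAE with onset after the last dose, recorded with the not-applicable action, is counted as leading to permanent discontinuation although it cannot have done so. That departs from the protocol's basis of events reported as the cause of cessation, and SAP 9.5, which attributes the changed analyses to the decision to end the trial, does not explain it.

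The importance is minor. The documents report no deaths, so the effect may be zero. If it occurs, one patient not otherwise counted adds 1.2 points at the planned 84 per arm, and more in the curtailed trial by an amount the documents do not allow us to fix. No hypothesis test is affected. The conclusion rests on reading the two criteria literally as alternatives and on investigators using the action field as Protocol 12.6 describes.

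**What to change.** In SAP 6.1.9.1, define the category as action *trial medication stopped*, or outcome *patient died* where the recorded action is not "Not applicable, patient is not taking IMP". State the condition on the action field. A cut-off on onset date is a different test and should not be offered as equivalent: an event can start on drug while IMP is stopped later for another reason.

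That clause leaves one case open: a fatal event that began on drug with action *dose not changed*, in a patient who completed dosing before dying. Two options would cover it:

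- Also require that the date of death is on or before the last dose, or immediately follows it.
- Use the action field alone, which is closest to the protocol's wording. Its price is that an on-drug death would drop out of the discontinuation table if the investigator did not record the drug as stopped.

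The cost is one sentence in the SAP and one condition in the program, or two if the date condition is added. No new data are needed for the basic clause, and no death is lost from the fatal TEAE summary.
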